3.2.2. PK Endpoint

- Plasma concentrations of PF-06651600 at Weeks 4 and 8 (or Week 12).

3.3. Baseline Variables

Baseline is defined as pre-dose on Day 1. Data from the screening period may be used if Day 1 data are missing. If multiple data points are available, we will use the observation closest but no later than Day 1.

For the analysis of ECG data, subject's baseline values will be the ECG assessment at the Screening visit. Data from the Day 1 may be used if screening data are missing.

3.4. Safety Endpoints

The safety endpoints are:

- Incidence of treatment-emergent adverse events (AEs).
- Incidence of serious AEs (SAEs) and AEs leading to discontinuation.
- The incidence of clinically significant abnormalities in vital signs.
- The incidence of clinically significant abnormalities in clinical laboratory values.

3.4.1. Adverse Events

An AE is considered a treatment emergent adverse event (TEAE) if the event starts on or after the first dosing day.

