Subjects will have up to 35 days of a screening period prior to the first dose of study drug to confirm that they meet the subject selection criteria for the study. The investigator (or an appropriate delegate at the investigator site) will obtain informed consent from each subject (or parent(s)/legal guardian and assent from the subject, as appropriate) in accordance with the procedures described in the [Schedule of Activities](#) section.

Due to possible need for tuberculin testing and chest radiograph, as well as to allow time for verification of SALT scores, screening procedures may be performed over more than 1 visit within the 35 days prior to the Day 1 visit.

Screening laboratory tests with abnormal results may be repeated **once** to confirm abnormal results (with the same screening number); the last value will be used to determine eligibility. If results return to normal within the 5-week screening period, the subject may enter the study.

Sites may be permitted to re-screen subjects (with a new screening number) who initially do not meet eligibility criteria **once** following agreement with the Sponsor.

The following procedures will be completed:

- Obtain written informed consent (or parent(s)/legal guardian and assent from the subject, as appropriate).

- Register subject in Impala.
- Review Inclusion and Exclusion criteria.
- Administer patient reported outcome (PRO) questionnaire: Patient Health Questionnaire – 8 items (PHQ-8).
- Collect demography.
- Complete AA disease history includes collection of details of AA at Screening: AA background, AA history, AA diagnosis, pattern of scalp hair loss, body hair loss, nail involvement, the use of topical treatments, systemic treatments and other treatments for AA used at any time prior to the Screening visit.
- Complete medical history, in addition to AA history, including but not limited to comorbidities associated with AA, history of drug, alcohol, tobacco use, skin rash, and infection will be collected at Screening. Smoking status and alcohol consumption will also be collected.
- Obtain complete medication history of all other prescription or nonprescription drugs, and dietary and herbal supplements taken within 35 days prior to the Screening Visit.
- Obtain vital signs: pulse rate, blood pressure, respiratory rate (after at least 5 minutes of rest), and temperature.
- Perform single 12-lead ECG.
- Obtain height and weight.

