### **8.1.4. Time Period for Collecting AE/SAE Information**

The time period for actively eliciting and collecting AEs and SAEs (“active collection period”) for each subject begins from the time the subject provides informed consent, which is obtained before the subject’s participation in the study (ie, before undergoing any study-related procedure and/or receiving investigational product), through and including a minimum of 28 calendar days; except as indicated below after the last administration of the investigational product.

For subjects who are screen failures, the active collection period ends when screen failure status is determined.

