#### **8.1.4.1. Reporting SAEs to Pfizer Safety**

All SAEs occurring in a subject during the active collection period are reported to Pfizer Safety on the CT SAE Report Form.

SAEs occurring in a subject after the active collection period has ended are reported to Pfizer Safety if the investigator becomes aware of them; at a minimum, all SAEs that the investigator believes have at least a reasonable possibility of being related to investigational product must be reported to Pfizer Safety.

Follow-up by the investigator continues throughout and after the active collection period and until the event or its sequelae resolve or stabilize at a level acceptable to the investigator, and Pfizer concurs with that assessment.

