#### **8.1.4.2. Recording Non-serious AEs and SAEs on the CRF**

During the active collection period, both non-serious AEs and SAEs are recorded on the CRF.

Follow-up by the investigator may be required until the event or its sequelae resolve or stabilize at a level acceptable to the investigator, and Pfizer concurs with that assessment.

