### 8.3. Severity Assessment

If required on the AE page of the CRF, the investigator will use the adjectives MILD, MODERATE, or SEVERE to describe the maximum intensity of the AE. For purposes of consistency, these intensity grades are defined as follows:	
MILD	Does not interfere with subject's usual function.
MODERATE	Interferes to some extent with subject's usual function.
SEVERE	Interferes significantly with subject's usual function.

Note the distinction between the severity and the seriousness of an AE. A severe event is not necessarily an SAE. For example, a headache may be severe (interferes significantly with the subject's usual function) but would not be classified as serious unless it met one of the criteria for SAEs, listed above.

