6.7.1. Adverse Events

The safety data will be summarized in accordance with Pfizer Standards. Adverse events of special interest will be summarized based on a list of preferred terms that will be provided by safety risk lead to the programming team prior to database lock. All safety data will be summarized descriptively through appropriate data tabulations, descriptive statistics, categorical summaries, and graphical presentations. Safety endpoints for the study include:

- Treatment-emergent (including treatment-related) AEs and SAEs;
- AEs leading to discontinuation;
- AEs will be displayed for the following periods: Baseline to Week 24, and Baseline to Week 48;
- Treatment-emergent COVID-19 related AEs by SOC and PT;
- Summary of TEAE before and after the COVID-19 pandemic anchor date.

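### The treatment-emergent definition rests on start date alone, so a pre-dose event that worsens on drug can go uncounted; its end and the scope of the SAE table are also left open

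*SAP*

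**What the plan says.** - **Definition.** SAP 3.4.1: "An AE is considered a treatment emergent adverse event (TEAE) if the event starts on or after the first dosing day". Neither document gives another definition, a clause for pre-dose events that worsen, or a last day.
- **When collection starts.** Under Protocol 8.1.4 it "begins from the time the subject provides informed consent". Protocol 6.1 adds: "Subjects will have up to 35 days of a screening period prior to the first dose of study drug".
- **When collection ends.** Protocol 8.1.4 continues it "through and including a minimum of 28 calendar days; except as indicated below after the last administration of the investigational product". On the CRF, Protocol 8.1.4.2 says: "During the active collection period, both non-serious AEs and SAEs are recorded on the CRF". For anything later, Protocol 8.1.4.1 says: "SAEs occurring in a subject after the active collection period has ended are reported to Pfizer Safety if the investigator becomes aware of them".
- **Severity.** Where the CRF asks for it, Protocol 8.3 uses a three-grade scale "to describe the maximum intensity of the AE".
- **Endpoints and tables.** SAP 3.4 puts TEAE incidence first. It then lists SAEs and discontinuation AEs as a separate item, with no treatment-emergent qualifier. SAP 6.7.1 names "Treatment-emergent (including treatment-related) AEs and SAEs", gives discontinuation AEs their own line, and displays AEs over two calendar periods, from baseline through Week 24 and through Week 48.

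**The concern.** A definition that looks only at the start date treats an event that was mild in screening and stayed mild the same as one that was mild in screening and became severe on drug. Neither counts. Protocol 1.7 names infection, including serious infection, and viral reactivation as potential risks, so on-drug worsening of an existing event is something the safety tables should be able to show. Because subjects are randomized, ongoing screening events should be balanced across arms on average. If the drug causes worsening, though, the uncounted events fall mainly on the active arms.

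The missing end works the other way. Off-drug time in early discontinuers can be credited to the assigned arm, and it is observed unevenly because later SAEs reach the sponsor only if the investigator hears of them.

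SAE counts may be small. Protocol 1.4.1 reports none in the first 24 weeks of the 48-subject Phase 2a arm on this drug. Whether a single pre-dose event that turned serious appears in the table could therefore be visible to a reader.

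**Working it through.** The plan states no figure to reproduce. The check sets the passages side by side and uses day arithmetic on the protocol's own windows.

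1. **Start of the window.** Consent opens collection and screening can last 35 days, so an AE record can carry an onset date as early as Day -35. Take one such event: mild in screening, ongoing at first dose, severe in Week 3.
   - Protocol 8.3 asks for one grade, the maximum, so the record reads severe.
   - SAP 3.4.1 looks at the onset date, which is before dosing. The record is not a TEAE, whatever its final grade.
   - If the site opens a second record at the worsening, that record has an on-treatment start date and is a TEAE.
   - No passage tells sites which to do. Protocol 8.2.1 gives worsening of the underlying disease as an example of an AE. Protocol 5.8 asks that medication changes be evaluated for new or worsening AEs. Neither says how a worsened AE is entered. Classification therefore depends on how the site records the event.

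2. **End of the window.** The follow-up visit is due within 28 (+7) days, so at the latest 28 + 7 = 35 days after the end-of-treatment or early-termination visit.
   - Completer: Day 337 + 7 (visit window) + 35 = Day 379.
   - Early discontinuer, assuming last dose and early-termination visit both on Day 57 (Week 8): minimum active collection runs to Day 57 + 28 = Day 85, and the follow-up visit is at the latest on Day 57 + 35 = Day 92.
   - Week 24 is Day 169 and Week 48 is Day 337. For that subject, 169 - 92 = 77 days of the first display period and 337 - 92 = 245 days of the second lie after the latest follow-up date. An event in that span that reaches the database meets SAP 3.4.1 and falls inside the display.
   - Such events can arrive because 28 days is a minimum, Protocol Appendix 3.2 allows further follow-up visits until resolution, Protocol 7.5.5 follows hearing decline off treatment, and late SAEs can be reported. Protocol 8.1.4.2 limits their number.
   - Subjects who roll over at once into the long-term study skip the follow-up period (Protocol 3). The SAP does not say where their window closes.

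3. **SAE table.** Take a pre-dose event that becomes serious on drug. Under SAP 3.4 it counts toward SAE incidence. If treatment-emergent in SAP 6.7.1 is read as qualifying both AEs and SAEs, it does not. Two programmers could follow the SAP and produce different tables.

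**The case against.** The best defence is that the event is not lost from the report. SAP 3.4 lists SAEs and discontinuation AEs without restriction. Protocol 9.5 adds severity of AEs, events triggering withdrawal, serious infections and adjudicated events, none limited to treatment-emergent ones. The mechanism is also conditional: Protocol 8.3 applies only if the CRF asks for severity, and the CRF instructions and the sponsor reporting standards cited in SAP 6.7 are not in the documents. Eligibility is rechecked on Day 1, and recent infections requiring treatment are excluded, which reduces the number of AEs ongoing at first dose. Finally, if one maximum grade is stored under one start date, a worsening rule cannot be programmed from those records alone.

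Much of this stands, and it rules out three stronger readings:

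- A reader might infer that pre-dose events turning serious drop out of the SAE tables. The documents do not establish that; only one reading of SAP 6.7.1 leads there.
- A reader might infer that events long after the last dose are routinely counted. CRF recording is tied to the active collection period, and no passage says that later SAEs enter the CRF.
- A reader might object that an event on Day 1 before the first tablet counts as treatment-emergent. Counting the whole first dosing day is inclusive and identical in every arm, and no passage shows that AE onset times are collected. That part of the rule should stay.

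The defence does not reach the TEAE endpoint itself. There the SAP states an explicit rule, and that rule excludes the worsened record.

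**Conclusion.** The point holds in three limited parts. First, a pre-dose AE that worsens or becomes serious on drug, and is kept as one record, is excluded from TEAE incidence by the stated rule. Second, the definition has no end tied to Protocol 8.1.4, which leaves a small, unevenly observed set of off-drug events open to inclusion. Third, SAP 3.4 and 6.7.1 do not settle whether the SAE table is limited to treatment-emergent events.

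The documents give no rate of AEs ongoing at first dose and no rate of worsening, so the number of subjects affected cannot be derived. The conclusion assumes that sites sometimes keep one record for a worsened event and that the unseen sponsor standards do not override SAP 3.4.1. No efficacy analysis changes. It is still worth correcting, because the first listed safety endpoint is incompletely defined and Protocol 9 has the SAP finalized before database lock and unblinding.

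**What to change.** - **SAP 3.4.1.** Count an AE as treatment-emergent if it begins on the first dosing day or later, or begins earlier and then increases in severity or becomes serious on or after that day. Close the window at the end of the active collection period in Protocol 8.1.4, or at rollover into the long-term study if that comes first.
- **SAP 6.7.1.** State that the SAE and discontinuation tables include every event that becomes serious or leads to discontinuation on or after first dose and within that window, whatever the AE start date. List SAEs reported later separately. This also brings 6.7.1 into line with 3.4.
- **Data.** Add a CRF completion note, or a query, for the date of worsening of AEs ongoing at first dose. Where that date was not recorded, list the AEs that started before dosing and were ongoing at first dose, with their maximum severity, by arm.

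The cost is a few SAP sentences, one programming rule and the note or query. The real limit is that past worsening dates may not be recoverable; the listing covers those cases.

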3.4.2. Laboratory Data

See Table 3 in the protocol for the list of clinical laboratory tests to be performed. Laboratory data Criteria for discontinuation and abnormalities are specified in [Section 9.3](#).

3.4.3. Vital Signs, Including Height and Weight

Vital sign measurements are pulse rate, blood pressure.

Height and weight are also collected pre- and post-treatment.

3.4.4. Physical Examinations

Complete physical examinations consist of assessments of general appearance; skin (dermatological full body exam); head, eyes, ears, nose, and throat (HEENT); mouth, heart; lungs; abdomen; extremities; neurologic function, back, and lymph nodes. Targeted physical examinations should include skin, heart, lung, and abdomen, neurologic function, and examination of body systems where there are symptom complaints by the subject.

3.4.5. Electrocardiogram (ECG)

ECG measurements will be collected at Screening, Day 1, Week 4, Week 24, Week 28, and Week 48.

4. ANALYSIS SETS

Data for all subjects will be assessed to determine if subjects meet the criteria for inclusion in each analysis population described below prior to unblinding and releasing the database and classifications will be documented per standard operating procedures.

4.1. Full Analysis Set

The Full Analysis Set (FAS) is defined as all subjects who have been randomized, regardless of whether they received study medication. Subjects will be analyzed in the treatment groups as they are randomized. If a subject was randomized but received the incorrect treatment, then the subject will be reported under their randomized treatment group for all efficacy analyses. If a subject is treated but not randomized, then the subject will be excluded from the FAS.

4.2. Per Protocol Analysis Set

The Per Protocol Analysis Set (PPAS) is defined as all randomized subjects who do not have any major protocol deviation related to inclusion/exclusion criteria, compliance with investigational product, or any other major protocol deviations that might affect the efficacy data through Week 24. The following deviations will be evaluated for each subject prior to unblinding to determine if a subject should be excluded from the PPAS:

1. Subject did not meet the following inclusion criteria for hair loss due to AA at Screening or Day 1:
 - a. Clinical diagnosis of AA with no other known etiology of hair loss, including no known androgenetic alopecia;
 - b. $\geq 50\%$ scalp hair loss;
 - c. Current episode of hair loss ≤ 10 years duration at time of Screening;
 - d. No evidence of terminal scalp hair regrowth within 6 months at both the screening and baseline visits.
2. Subject met one of the following exclusion criteria regarding medical history diagnoses:
 - a. Another scalp disease which could impact hair loss assessments;
 - b. Active systemic disease which can cause hair loss.
3. Subjects who were randomized but never received study drug.
4. Prior to the date of the Week 24 visit, subject had a dosing interruption of ≥ 6 weeks for any reason.
5. Prior to the date of the Week 24 visit, subject used a prior or concomitant prohibited medication that could potentially impact efficacy data at Week 24.

6. Week 24 SALT assessment was impacted in one of the following ways:
 - a. Visit/assessment was not performed;
 - b. Assessment was not performed properly (including subject had a shaved head).
7. Subjects with other major protocol deviations not listed above that, in the opinion of the sponsor study team, could potentially impact efficacy data at Week 24.

The subjects excluded from this analysis set will be determined and documented before the study is unblinded.

4.3. Safety Analysis Set

The Safety Analysis Set (SAS) will be defined as all subjects who receive at least one dose of study medication. The safety analysis set is the primary population for treatment administration/compliance and safety. A randomized but not treated subject will be excluded from the safety analyses. If a subject was randomized but received partially incorrect treatment, then the subject will be summarized under the treatment received for most of the time during the study, for all safety analyses.

5. GENERAL METHODOLOGY AND CONVENTIONS

The final analysis and reporting of results will be performed after the completion of the study and after the database is locked.

5.1. Hypotheses and Decision Rules

This section describes the testing procedure for multiple comparisons. This CCI [REDACTED] will support submission in several regions with different requirements; therefore, this section is organized into 3 sections: [Section 5.1.1](#) describes the testing procedure for the overall study, [Section 5.1.2](#), for the FDA/PMDA, and [Section 5.1.3](#) for the EMA and competent authorities in the VHP countries.

The study is tested at an overall $\alpha = 0.05$. While the 5% significance level is deemed sufficient for a declaration of effect, more stringent levels have been advised for regulatory submission of B7981015 CCI [REDACTED], ie, 1% for EMA and competent authorities in the VHP countries, and 0.125% for the FDA/PMDA.

The hypotheses to be tested are that each of the active treatment groups (200 mg QD/50 mg QD, 50 mg QD/50 mg QD, 200 mg QD/30 mg QD, and 30 mg QD/30 mg QD) is superior to placebo as measured by the proportion of subjects achieving the primary endpoint at Week 24 and key secondary endpoints where applicable.

The grouping of the dose regimens in the test hierarchy was based on the hierarchy of 2 different dose regimens: in the dosing regimens that have a loading dose, the order is 200 mg QD/50 mg QD → 200 mg QD/30 mg QD; in the regimens without a loading dose, the order is 50 mg QD/50 mg QD → 30 mg QD/30 mg QD. The testing strategy proposed will allow simultaneous testing of the 200 mg QD/30 mg QD and the 50 mg QD/50 mg QD dose regimens against placebo, given that it is not known which dose regimen will have a better response.

5.1.1. Overall Study (Testing Procedure for Multiple Comparisons Incorporating the SALT ≤ 10 as a Key Secondary Endpoint)

For the overall study the SALT ≤ 20 response at Week 24 is the primary endpoint and the SALT ≤ 10 response at Week 24 will be analyzed as a key secondary endpoint. The hypotheses to be tested are that each of the active treatment groups is superior to placebo as measured by the proportion of subjects achieving the primary endpoint and the key secondary endpoint. There are a total of 8 hypotheses to be tested:

- Hypothesis 1 (H1) is to test whether the 200 mg QD/50 mg QD dose regimen is superior to placebo for the primary endpoint;
- Hypothesis 2 (H2) is to test whether the 50 mg QD dose regimen is superior to placebo for the primary endpoint;
- Hypothesis 3 (H3) is to test whether the 200 mg QD/30 mg QD dose regimen is superior to placebo for the primary endpoint;

- Hypothesis 4 (H4) is to test whether the 30 mg QD dose regimen is superior to placebo for the primary endpoint;
- Hypothesis 1p (H1p) is to test whether the 200 mg QD/50 mg QD dose regimen is superior to placebo for the key secondary endpoint;
- Hypothesis 2p (H2p) is to test whether the 50 mg QD dose regimen is superior to placebo for the key secondary endpoint;
- Hypothesis 3p (H3p) is to test whether the 200 mg QD/30 mg QD dose regimen is superior to placebo for the key secondary endpoint;
- Hypothesis 4p (H4p) is to test whether the 30 mg QD dose regimen is superior to placebo for the key secondary endpoint.

The family-wise Type I error will be strongly controlled using a gatekeeping approach as described in the following order and shown in [Figure 2](#). The 10 mg group comparison to placebo is not included in the Type I error controlled procedure, as this group is only included to support the estimation of the exposure response.

[figure not shown]
- The primary endpoint for 200 mg QD/50 mg QD dose regimen (H1) will be tested at α significance level first. If significant, then the primary endpoint for 50 mg QD dose regimen and the 200 mg QD/30 mg QD dose regimen (H2 and H3) and the key secondary endpoint for 200 mg QD/50 mg QD dose regimen (H1p) will be tested simultaneously. If both the 50 mg QD dose regimen and the 200 mg QD/30 mg QD dose regimen are significant, then the 30 mg QD dose regimen will be tested.
- For the primary endpoint, if both the 50 mg QD dose regimen and the 200 mg QD/30 mg QD dose regimen are significant at $\alpha/4$ level, or if one of the dose regimens (50 mg QD dose regimen or 200 mg QD/30 mg QD dose regimen) is significant at $\alpha/4$ level and the other is significant at $\alpha/2$ level, both dose regimens will be declared as significant. In this case, the 30 mg QD dose regimen will be tested at $\alpha/2$ level. If only one of the regimens (50 mg QD dose regimen or 200 mg QD/30 mg QD dose regimen) is significant at $\alpha/4$ level and the other is not significant at $\alpha/2$ level, only the one significant at $\alpha/4$ level will be declared as statistically significant. In this case, the testing for the 30 mg QD dose regimen will not proceed.
- For the key secondary endpoint, the 200 mg QD/50 mg QD dose regimen will be tested at $\alpha/2$ level first. If significant, then the 50 mg QD dose regimen and the 200 mg QD/30 mg QD dose regimen will be tested simultaneously. If both the 50 mg QD dose regimen and the 200 mg QD/30 mg QD dose regimen are significant at $\alpha/4$ level, or if one of the dose regimens (50 mg QD dose regimen or 200 mg QD/30 mg QD dose regimen) is significant at $\alpha/4$ level and the other is significant at $\alpha/2$ level, both dose regimens will be declared as significant. In this case, the 30 mg QD dose regimen will be tested at $\alpha/2$ level. If only one of the

regimens (50 mg QD dose regimen or 200 mg QD/30 mg QD dose regimen) is significant at $\alpha/4$ level and the other is not significant at $\alpha/2$ level, only the one significant at $\alpha/4$ level will be declared as statistically significant. In this case, the resting for the 30 mg QD dose regimen will not proceed.

- If the primary endpoint for the 200 mg QD/50 mg QD dose regimen is significant at α level, and all the remaining hypotheses for the primary endpoint and key secondary endpoint are significant at the overall $\alpha/2$ level, then all 8 hypotheses will be declared as statistically significant.
- If the primary endpoint for all 4 hypotheses or the primary endpoint for H1 is significant and the key secondary endpoint is significant in all 4 hypotheses, then the $\alpha/2$ level will be passed to the hypothesis testing for the other hypotheses. In this case, the other hypotheses can be tested at the α level instead of the $\alpha/2$ level following the same procedures for claiming statistical significance outlined in the bullets above with the exception of the increased α .

Figure 2. Schematic and Graphical Presentation for Multiple Testing Procedure Incorporating a Key Secondary Endpoint

The numbers on each edge indicate the transition rule for the weights on α allocation once a hypothesis is rejected.

The following approach will be used to control the Type I error for SALT ≤ 20 at earlier time points:

- For a given dose, if the primary endpoint of SALT ≤ 20 is declared to be statistically significant based on the testing procedure for the primary endpoint, in order to establish the onset of efficacy as measured by SALT ≤ 20 at the earliest time point, a step-down approach with SALT ≤ 20 from Week 24 to earlier time points (order of testing: Weeks 24, 18, 12, 8, and 4) will be used for each time point. Although this testing scheme does not protect the Type I error for the family of all possible comparisons, it will provide Type I error protection for testing the family of SALT ≤ 20 time points within the same dose group.

5.1.2. For the FDA/PMDA (Testing Procedure for Multiple Comparisons with no Key Secondary Endpoints)

[figure not shown]
For the FDA/PMDA, the SALT ≤ 20 response at Week 24 is the primary endpoint and no secondary endpoints will be analyzed as key secondary. The hypotheses to be tested at $\alpha = 0.00125$ are that each of the active treatment groups is superior to placebo as measured by the proportion of subjects achieving the primary endpoint. There are a total of 4 hypotheses to be tested.

- Hypothesis 1 (H1) is to test whether the 200 mg QD/50 mg QD dose regimen is superior to placebo for the primary endpoint;
- Hypothesis 2 (H2) is to test whether the 50 mg QD/50 mg QD dose regimen is superior to placebo for the primary endpoint;
- Hypothesis 3 (H3) is to test whether the 200 mg QD/30 mg QD dose regimen is superior to placebo for the primary endpoint;
- Hypothesis 4 (H4) is to test whether the 30 mg QD/30 mg QD dose regimen is superior to placebo for the primary endpoint.

The family-wise Type I error will be strongly controlled using a gate-keeping approach to test these hypotheses in 3 groups as shown in Figure 3. The first group includes H1; the second group includes H2 and H3; and the third group includes H4. The statistical significance of the first hypothesis (H1) will allow simultaneous testing of H2 and H3 using Holm's method. Statistical significance for both H2 and H3 will enable testing the statistical significance for the fourth hypothesis (H4). The 10 mg group comparison to placebo is not included in the Type I error controlled procedure, as this group is only included to support the estimation of the exposure response.

Figure 3 shows a schematic of the procedure for testing each of the active treatment groups versus the placebo group for the primary endpoint.

Figure 3. Schematic and Graphical Presentation for Multiple Testing Procedure

The numbers on each arrow indicate the transition rule for the weights on α allocation once a hypothesis is rejected.

In the simultaneous testing of H2 and H3, if both the 50 mg QD/50 mg QD and 200 mg QD/30 mg QD regimens are not significant at $\alpha/2$ level, the test for statistical significance is stopped. If one of the hypotheses for 50 mg QD/50 mg QD and 200 mg QD/30 mg QD regimens is significant at $\alpha/2$ level and the other hypothesis is significant at α level, this family hypothesis is significant. If one of the hypotheses for 50 mg QD/50 mg QD and 200 mg QD/30 mg QD is significant at $\alpha/2$ level and the other hypothesis is not significant at α level, only the hypothesis significant at $\alpha/2$ level will be declared as statistically significant. In this case, the testing for statistical significance for H4 will not proceed.

The following approach will be used to control the Type I error for testing SALT ≤ 10 at Week 24:

- For a given dose, if SALT ≤ 20 at Week 24 is declared to be statistically significant based on the testing procedure for the primary endpoint(s), then SALT ≤ 10 at Week 24 will be tested at the same significance level as the SALT ≤ 20 at Week 24 was tested. Though this testing scheme does not protect the Type I error for the family of all possible comparisons, it will provide Type I error protection for testing the endpoints within the same dose group.

The following approach will be used to control the Type I error for testing SALT ≤ 20 at earlier time points:

- For a given dose, if the primary endpoint of SALT ≤ 20 at Week 24 is declared to be statistically significant based on the testing procedure for the primary endpoint, in order to establish the onset of efficacy as measured by SALT ≤ 20 at the earliest time point, a step-down approach with SALT ≤ 20 from Week 24 to earlier time points (order of testing: Weeks 24, 18, 12, 8, and 4) will be used for each time point. Though this testing scheme does not protect the Type I error for the family of all possible comparisons, it will provide Type I error protection for testing the family of SALT ≤ 20 time points within the same dose group.

5.1.3. For the EMA and Competent Authorities in the VHP Countries (Testing Procedure for Multiple Comparisons Incorporating the PGI-C Response as a Key Secondary Endpoint)

For the EMA and competent authorities in the VHP countries, the SALT ≤ 10 response at Week 24 will be the primary endpoint and the PGI-C response at Week 24 will be analyzed as a key secondary endpoint. The hypotheses to be tested at $\alpha = 0.01$ are that each of the active treatment groups is superior to placebo as measured by the proportion of subjects achieving the primary endpoint and the key secondary endpoint. There are a total of 8 hypotheses to be tested:

- Hypothesis 1 (H1) is to test whether the 200 mg QD/50 mg QD dose regimen is superior to placebo for the primary endpoint;
- Hypothesis 2 (H2) is to test whether the 50 mg QD dose regimen is superior to placebo for the primary endpoint;
- Hypothesis 3 (H3) is to test whether the 200 mg QD/30 mg QD dose regimen is superior to placebo for the primary endpoint;
- Hypothesis 4 (H4) is to test whether the 30 mg QD dose regimen is superior to placebo for the primary endpoint;
- Hypothesis 1p (H1p) is to test whether the 200 mg QD/50 mg QD dose regimen is superior to placebo for the key secondary endpoint;
- Hypothesis 2p (H2p) is to test whether the 50 mg QD dose regimen is superior to placebo for the key secondary endpoint;
- Hypothesis 3p (H3p) is to test whether the 200 mg QD/30 mg QD dose regimen is superior to placebo for the key secondary endpoint;
- Hypothesis 4p (H4p) is to test whether the 30 mg QD dose regimen is superior to placebo for the key secondary endpoint.

The family-wise Type I error will be strongly controlled using a gate-keeping approach as described in the following order and shown in [Figure 2](#). The 10 mg group comparison to placebo is not included in the Type I error controlled procedure, as this group was only included in the study design to support the estimation of the exposure response.

- The primary endpoint for 200 mg QD/50 mg QD dose regimen (H1) will be tested at α significance level first. If significant, then the primary endpoint for 50 mg QD dose regimen and the 200 mg QD/30 mg QD dose regimen (H2 and H3) and the key secondary endpoint for 200 mg QD/50 mg QD dose regimen (H1p) will be tested simultaneously. If both the 50 mg QD dose regimen and the 200 mg QD/30 mg QD dose regimen are significant, then the 30 mg QD dose regimen will be tested.
- For the primary endpoint, if both the 50 mg QD dose regimen and the 200 mg QD/30 mg QD dose regimen are significant at $\alpha/4$ level, or if one of the dose regimens (50 mg QD dose regimen or 200 mg QD/30 mg QD dose regimen) is significant at $\alpha/4$ level and the other is significant at $\alpha/2$ level, both dose regimens will be declared as significant. In this case, the 30 mg QD dose regimen will be tested at $\alpha/2$ level. If only one of the regimens (50 mg QD dose regimen or 200 mg QD/30 mg QD dose regimen) is significant at $\alpha/4$ level and the other is not significant at $\alpha/2$ level, only the one significant at $\alpha/4$ level will be declared as statistically significant. In this case, the testing for the 30 mg QD dose regimen will not proceed.
- For the key secondary endpoint, the 200 mg QD/50 mg QD dose regimen will be tested at $\alpha/2$ level first. If significant, then the 50 mg QD dose regimen and the 200 mg QD/30 mg QD dose regimen will be tested simultaneously. If both the 50 mg QD dose regimen and the 200 mg QD/30 mg QD dose regimen are significant at $\alpha/4$ level, or if one of the dose regimens (50 mg QD dose regimen or 200 mg QD/30 mg QD dose regimen) is significant at $\alpha/4$ level and the other is significant at $\alpha/2$ level, both dose regimens will be declared as significant. In this case, the 30 mg QD dose regimen will be tested at $\alpha/2$ level. If only one of the regimens (50 mg QD dose regimen or 200 mg QD/30 mg QD dose regimen) is significant at $\alpha/4$ level and the other is not significant at $\alpha/2$ level, only the one significant at $\alpha/4$ level will be declared as statistically significant. In this case, the testing for the 30 mg QD dose regimen will not proceed.
- If the primary endpoint for the 200 mg QD/50 mg QD dose regimen is significant at α level, and all the remaining hypotheses for the primary endpoint and key secondary endpoint are significant at the overall $\alpha/2$ level, then all 8 hypotheses will be declared as statistically significant.
- If the primary endpoint for all 4 hypotheses or the primary endpoint for H1 is significant and the key secondary endpoint is significant in all 4 hypothesis, then the $\alpha/2$ level will be passed to the hypothesis testing for the other hypotheses. In this case, the other hypotheses can be tested at α level instead of the $\alpha/2$ level following the same procedures for claiming statistical significance outlined in the bullets above with the exception of the increased α .

For the EMA and competent authorities in the VHP countries, the following approach will be used to control the Type I error for SALT ≤ 20 at Week 24:

- For a given dose, if $SALT \leq 10$ at Week 24 is declared to be statistically significant based on the testing procedure for the primary endpoint incorporating the key secondary endpoint, then $SALT \leq 20$ at Week 24 will be tested at the same significance level as $SALT \leq 10$ at Week 24 was tested. Although this testing scheme does not protect the Type I error for the family of all possible comparisons, it will provide Type I error protection for testing the endpoints within the same dose group.

The following approach will be used to control the Type I error for $SALT \leq 10$ at earlier timepoints:

- For a given dose, if the primary endpoint of $SALT \leq 10$ is declared to be statistically significant based on the testing procedure for the primary endpoint incorporating the key secondary endpoint, in order to establish the onset of efficacy as measured by $SALT \leq 10$ at the earliest time point, a step-down approach with $SALT \leq 10$ from Week 24 to earlier time points (order of testing: Weeks 24, 18, 12, 8, and 4) will be used for each time point. Although this testing scheme does not protect the Type I error for the family of all possible comparisons, it will provide Type I error protection for testing the family of $SALT \leq 10$ time points within the same dose group.

